## 2. OBJECTIVES AND ENDPOINTS

• Objectives	• Endpoints
• Primary	
• To evaluate feasibility of dynamic implementation (DI) compared to routine implementation (RI) for APRETUDE administration.	• Staff study participants' (SSPs) mean Feasibility of Intervention Measure (FIM) score at M13  .
• Secondary	•
• To evaluate change in feasibility of RI and DI for APRETUDE administration	• Change from baseline in SSPs' FIM score at M5 and M13. • SSPs perceptions of facilitators and barriers to RI and DI and overall implementation of PrEP into routine care assessed through M13.
• To evaluate feasibility and acceptability of APRETUDE for MSM and TGM.	• Patient Study Participants' (PSPs) mean FIM and Acceptability of Intervention Measure (AIM) scores as well as implementation science questionnaire (ISQ) responses at BL, M7(OLI)/M6(DTI) and M13(OLI)/M12(DTI). • Change from baseline in PSPs' AIM and FIM scores as well as ISQ responses FIM score at M7(OLI)/M6(DTI) and M13(OLI)/M12(DTI). • PSPs perception of facilitators and barriers to feasibility and acceptability of APRETUDE through M13(OLI)/M12(DTI).
• To evaluate feasibility and acceptability of telehealth delivery for APRETUDE administration by clinical staff.	• SSPs' mean FIM and AIM scores as well as ISQ responses for telehealth delivery at BL, M5 and M13. • Change from baseline in SSPs' FIM and AIM score as well as ISQ responses for telehealth delivery at M5 and M13 .

• Objectives	• Endpoints
	
 
• PSPs' mean FIM and AIM scores as well as ISQ responses for telehealth delivery at BL, M7(OLI)/M6(DTI) and M13(OLI)/M12(DTI)
 
• Change from baseline in PSPs' FIM and AIM scores as well as ISQ responses for telehealth delivery at M7(OLI)/M6(DTI) and M13(OLI)/M12(DTI).
 
• SSPs and PSPs perception of facilitators and barriers to feasibility and acceptability of telehealth use through M13 and M13(OLI)/M12(DTI) respectively.
 

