### 3.3.2. SSPs

SSPs will complete assessments as outlined in [ANNEX 1](#) and agree to data privacy requirements prior to the completion of study assessments. Assessments will include questionnaires and interviews at baseline, M5 and M13; baseline questionnaires with SSPs should be completed prior to the enrolment of the first participant at their site, which might vary by site depending on whether the first PSP started CAB PrEP with or without optional OLI. They will also participate in monthly FRAME-IS assessments. Sites in the DI arm will participate in quarterly group and monthly one-on-one facilitation calls.

The PrEP provider at the site will manage and remain responsible for all clinical aspects of the PSPs enrolled at the site during the study.

- During the screening period, the site will obtain the PSP's informed consent and confirm inclusion and exclusion criteria prior to enrolling in the study/M1. The site will also complete demography and vital signs and required labs per clinical local standard of care.
- (See SoA for specific laboratory test results that should be documented in the eCRF, e.g., HIV testing results and any positive STI clinical diagnoses (defined for this study as syphilis (any stage), gonorrhea, chlamydia, or trichomonas) at Screening and at any time point during the study, laboratory abnormalities associated with AEs leading to study discontinuations, positive pregnancy test results). The site will explain to the PSPs that medical records may be requested from other medical facilities to support complete reporting of SAEs or other events if they occur during the study.
- For PSPs diagnosed with incident HIV-1 infections (defined as newly diagnosed HIV infection following enrolment and during the study), the site may perform additional tests, including but not limited to HIV-1 viral load, CD4 count, genotype/phenotype tests, and recency assays, and initiate antiretroviral therapy (ART) as per the site's standard of care. See SoA for collection of available results as well as the start date of ART and classes of ART regimen used for PSPs with incident HIV-1 infection.
- The PrEP provider at the site will prescribe CAB tablets for PrEP to PSPs who will receive optional OLI and administer APRETUDE IM injections as per approved prescribing information.

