**Table 3 Implementation Assessments**

Outcome	Assessment Level	Measurement	OLI/DTI Time point
Feasibility-Overall	Staff Study Participants	FIM	BL, M5, M13
		Staff ISQ	BL, M5, M13
		SSI	M5, M13
	Patient Study Participants	FIM	M13(OLI)/M12(DTI)
		Patient ISQ	BL, M7(OLI)/M6(DTI), M13(OLI)/M12(DTI)
		SSI	BL, M7(OLI)/M6(DTI), M13(OLI)/M12(DTI)
Acceptability-Overall	Staff Study Participants	AIM	BL, M5, M13
		SSI	M5, M13
Feasibility - Telehealth	Staff Study Participants	FIM	BL, M5, M13
		SSI	M5, M13
		Staff ISQ	BL, M5, M13
	Patient Study Participants	FIM	BL, M7(OLI)/M6(DTI), M13(OLI)/M12(DTI)
		SSI	BL, M7(OLI)/M6(DTI), M13(OLI)/M12(DTI)
		Patient ISQ	BL, M7(OLI)/M6(DTI), M13M13(OLI)/M12(DTI)
Acceptability - Telehealth	Staff Study Participants	AIM	BL, M5, M13
		SSI	M5, M13
		Staff ISQ	BL, M5, M13
	Patient Study Participants	AIM	BL, M7(OLI)/M6(DTI), M13(OLI)/M12(DTI)
		SSI	BL, M7(OLI)/M6(DTI), M13M13(OLI)/M12(DTI)
	Patient ISQ	BL, M7(OLI)/M6(DTI), M13(OLI)/M12(DTI)	
Acceptability – Cabotegravir LA	Patient Study Participants	AIM	BL, M7(OLI)/M6(DTI), M13(OLI)/M12(DTI)

Outcome	Assessment Level	Measurement	OLI/DTI Time point
		SSI	BL, M7(OLI)/M6(DTI), M13(OLI)/M12(DTI)
		Patient ISQ	BL, M7(OLI)/M6(DTI), M13(OLI)/M12(DTI)
Fidelity	Patient Study Participants	Adherence to Target date ( $\pm 7$ days), eCRF	Monthly
		Patient ISQ	BL, M7(OLI)/M6(DTI), M13(OLI)/M12(DTI)
		SSI	BL, M7(OLI)/M6(DTI), M13(OLI)/M12(DTI)
	Staff Study Participants	Staff ISQ	BL, M5, M13
		SSI	BL, M5, M13
		# clinical staff-initiated assessments/ # eligible pts	Monthly
	Cross Study 	Composite measure*: • adherence to target date • assessments given • missed appointments	BL-M13
Reach	Staff Study Participants	# pts receiving 1st injection / #eligible pts based on assessments	Monthly
Awareness	Staff Study Participants	Assessment tool	Monthly
		Staff ISQ	BL, M5
		SSI	BL, M5
	Patient Study Participants	Assessment tool	BL
		Patient ISQ	BL
Uptake	Staff Study Participants	Assessment tool	Monthly
		Clinic administrative records	Monthly
		Staff ISQ	BL, M5, M13
	Patient Study Participants	Assessment tool	Monthly
		Patient ISQ	BL
Persistence, Retention	Staff Study Participants	Assessment tool	Monthly
		Clinic administrative records	Monthly
		Adherence to Target date ( $\pm 7$ days), admin records	Monthly
		Staff ISQ	BL, M5, M13
	Patient Study Participants	Adherence to Target date ( $\pm 7$ days), eCRF	Monthly
Process evaluation of implementation		Patient ISQ	M7(OLI)/M6(DTI), M13(OLI)/M12(DTI)

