**4.1.3.1. Timepoint Definitions for Completion of Questionnaires and Interviews****PSPs:**

- PSPs who are started on oral Cabotegravir PrEP as optional OLI will receive their first dose of oral CAB in Month 1. PSPs who are started on APRETUDE injections (direct to injection) will receive their first dose of APRETUDE injection in Month 1.
- Each administration of APRETUDE injection will be categorized by the sequential number, e.g., Dose 1 visit (first injection), Dose 2 visit (second injection); and the corresponding Study Month will be recorded.
- Baseline IS assessment is defined as the first assessment taken on or before receiving Dose 1 of APRETUDE injection. Baseline questionnaires should be completed within two weeks of or on their Dose 1 visit and before receiving the first APRETUDE injections.
- For each PSP, the last APRETUDE injection is to occur at the last study visit.
- All study visits, including those where questionnaires and/or interviews are administered at M7(OLI)/M6(DTI) and M13(OLI)/M12(DTI), will be anchored off of each PSP M1, so it reflects months in study, regardless of what dose they are on and regardless of whether they have missed any injections and received oral CAB tablets for PrEP.
- Approximately 3 PSPs per site will participate in SSIs; number of SSIs might vary by site. Participants will be purposely sampled for interviews based on demographic characteristics, such as race/ethnicity, prior PrEP use.
- Interviews should be conducted with all PSPs who discontinue participation within one month of discontinuation, when possible.

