**Figure 7 Relationship between Minimum Sample Size Required for RI Arm and the Assumed Standardized Effect Size for PSPs**

### 5.3. Essential Analysis

The primary endpoint in terms of feasibility is SSPs' mean FIM score at Month 13 under Dynamic Implementation (DI) arm and Routine Implementation (RI) arm respectively, and the difference of their mean FIM scores between arms. For FIM of SSPs and the difference between arms, descriptive statistics including 95% confidence intervals will be displayed for these estimates. Mean FIM scores will be compared between the two implementation arms to test if the observed difference is statistically significant. In

addition, distribution of FIM items scores will also be compared. P-values will be reported for these comparisons.

To address the potential intra-cluster correlation effect due to the cluster randomization design, classical methods such as mixed effects linear regression model or Generalized Estimating Equations will be utilized. Besides the analysis on the subject level, the stratification analysis will be performed at the site level to evaluate the impact of the capacity of sites (high volume vs low volume) in responses to two implementation strategies imposed on SSPs. Exploratory analysis will be undertaken to assess the variability of responses by other factors such as subset of implementation strategies.

In addition to summary of mean FIM scores of SSPs at different timepoints, the change in mean FIM scores from baseline will be analyzed at the designated timepoints. For the specific Telehealth implementation strategy on SSPs, the subgroup analysis on FIM scores including change from baseline will be conducted.

The FIM scores of PSPs will be summarized in the same way as those of SSPs. In addition, subgroup analysis on PSPs will include, but not limited to, factors such as demographic, baseline characteristics, study arm, clinic characteristics and APRETUDE initiation method. To address the potential differential dropout rates of PSPs between arms, appropriate imputation methods will be undertaken to handle missing data of different type.

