## 5.4. Secondary Analysis

Key secondary outcomes include

- Acceptability and feasibility of telehealth delivery: The mean Acceptability of Intervention Measure (AIM) score and Feasibility of Intervention Measure (FIM) score for SSPs and PSPs will be calculated. The scores will be calculated at Baseline, Month 5 and Month 13 for SSPs, and at Baseline, Month 7 (OLI)/Month 6(DTI), and Month 13(OLI)/Month 12(DTI) for PSPs. Change from Baseline of mean score in the AIM and FIM scores at the respective time points from SSPs and PSPs will also be calculated. Descriptive statistics will be used including 95% confidence intervals. Exploratory analyses will be undertaken to assess the variability of responses by factors including but not limited to clinic characteristics, SSP role and study arm.

Additional analyses will assess SSPs and PSPs responses to acceptability and feasibility questions posed in the IS questionnaires. The finalization of the questionnaires will inform the latter analyses.

Other secondary outcomes to evaluate include:

- Change from baseline in SSPs' FIM score of RI and DI for APRETUDE administration over time

- SSPs perceptions of facilitators and barriers to RI and DI and overall implementation of PrEP into routine care assessed over time
- PSPs mean FIM and AIM score as well as ISQ responses for APRETUDE over time
- Change from baseline in PSPs' AIM score and FIM score as well as ISQ responses for APRETUDE over time
- PSPs perception of facilitators and barriers to feasibility and acceptability of APRETUDE over time'
- SSPs' mean AIM score and ISQ responses for RI and DI for APRETUDE administration over time
- Change from baseline in SSPs' AIM score and ISQ responses for RI and DI for APRETUDE administration over time
- PSPs' mean AIM score and ISQ responses by implementation strategy over time
- Change from baseline in PSPs' mean AIM score and ISQ responses by implementation strategy over time
- Proportion of SSPs and PSPs that agree or completely agree on the ISQ that each implementation strategy is fit for use over time
- SSPs and PSPs perceptions of utility of implementation strategies and PSPs perceptions of facilitators and barriers to acceptability of RI and DI over time
- Proportion of injections occurring within target window from target date ( $\pm$  7 days for Injection dose 2 and  $\pm$  7 days of target date for subsequent injections) over time
- Proportion of PSPs completing target number of injections through M13

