Procedure 	Screening/ Enrollment Up to 90 days 	Treatment Period  Month(M)/Dose(D)												E.D. 	Notes
		M1	M2	M3	M4	M5	M6	M7	M8	M9	M10	M11	M12		
		D1  visit	D2 visit		D3 visit		D4 visit		D5 visit		D6 visit		D7 visit		
Cabotegravir LA PrEP IM Maintenance injections			X		X		X		X		X		X		IM dosing is expected to occur on the same date of the month as determined by Dose 1 - Treatment Target Date. Dosing window is (+ or -) a 7-day window, as per the USPI.
Concomitant medication review	X													X	Record in CRF if; contraindicated medications, concomitant medications with a potential for a drug-drug interaction (DDI) per the CAB tablet for PrEP or APRETUDE USPI;

Procedure 	Screening/ Enrollment Up to 90 days 	Treatment Period  Month(M)/Dose(D)												E.D. 	Notes
		M1	M2	M3	M4	M5	M6	M7	M8	M9	M10	M11	M12		
		D1  visit	D2 visit		D3 visit		D4 visit		D5 visit		D6 visit		D7 visit		
Adverse Event (AE) Review		X												X	Only drug related AEs and AEs leading to CAB Prep discontinuation will be collected in the eCRF.
Serious AEs (SAEs)	X													X	All SAEs regardless of relatedness will be collected in the eCRF.
Pregnancy status	X													X	Ask person of childbearing potential at each visit if they are pregnant and ask for the date of their LMP.
Questionnaires and Interviews: Questionnaires and Interviews should be completed before receiving APRETUDE IM injections															

Procedure 	Screening/ Enrollment Up to 90 days 	Treatment Period  Month(M)/Dose(D)												E.D. 	Notes	
		M1	M2	M3	M4	M5	M6	M7	M8	M9	M10	M11	M12			
		D1  visit	D2 visit		D3 visit		D4 visit		D5 visit		D6 visit		D7 visit			
Patient Study Participants																
PSP baseline questionnaires should be completed within two weeks prior to or on their D1 visit and before receiving the 1 st APRETUDE injection.																

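### Table 3 gives patients' overall FIM at the last visit only, so the baseline, mid-study and change-from-baseline FIM endpoints in Section 2 would have no data

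*Protocol*

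**What the plan says.** **What is to be analysed.** In Section 2, the objective on feasibility and acceptability of APRETUDE for MSM and TGM asks for patients' mean FIM at baseline, M7(OLI)/M6(DTI) and M13(OLI)/M12(DTI). It also asks for "Change from baseline in PSPs' AIM and FIM scores as well as ISQ responses FIM score at M7(OLI)/M6(DTI) and M13(OLI)/M12(DTI"). Section 5.4 lists the same change outcome: "Change from baseline in PSPs' AIM score and FIM score as well as ISQ responses for APRETUDE over time". Section 5.3 adds: "The FIM scores of PSPs will be summarized in the same way as those of SSPs". In that section the staff summaries cover several time points and change from baseline.

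**What is to be collected.** Section 4.1.3 refers to Table 3 for the administration of assessments. Under Feasibility-Overall, the patient FIM row reads "Patient Study Participants FIM M13(OLI)/M12(DTI"), with no baseline and no mid-study visit. In the same block the patient questionnaire row reads "Patient ISQ BL, M7(OLI)/M6(DTI), M13(OLI)/M12(DTI").

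**When baseline is.** For patients, Section 4.1.3.1 states: "Baseline IS assessment is defined as the first assessment taken on or before receiving Dose 1 of APRETUDE injection". Annex 1 agrees: "PSP baseline questionnaires should be completed within two weeks prior to or on their D1 visit". Both Annexes place patient questionnaires at D1, M6/M7 and M12/M13, but neither names the instruments given at each visit.

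**A smaller mismatch in the same table.** For staff, Section 3.3.2 says: "Assessments will include questionnaires and interviews at baseline, M5 and M13". Neither Annex schedules a staff interview at baseline.

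**The concern.** The endpoint table and the analysis sections treat patients' overall FIM as a repeated measure. The assessment table treats it as a single end-of-study measure. Both cannot be right.

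This is a question of data collection, which an analysis plan cannot repair. A change score needs a baseline, and the protocol's own definition closes the baseline window at the first injection. Any patient who passes that point without completing FIM has no change score at either later visit. The mid-study gap also matters: Section 5 plans baseline analyses and an interim analysis at M7(OLI)/M6(DTI) for patients, and neither would contain patients' overall FIM.

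**Working it through.** **1. Is the short cell a damaged table?** The neighbouring patient ISQ and interview rows are intact and list three time points. The FIM cell is well formed, only shorter. The patient FIM and AIM rows in Table 3 are:

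| Table 3 row (patients) | Baseline | M7/M6 | M13/M12 |
|---|---|---|---|
| FIM, Feasibility-Overall | no | no | yes |
| FIM, Telehealth | yes | yes | yes |
| AIM, Telehealth | yes | yes | yes |
| AIM, Cabotegravir LA | yes | yes | yes |

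One row of four lacks the first two times.

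**2. Can the telehealth FIM row stand in?** No. It rates telehealth delivery, which Sections 4.1.2 and 4.1.5 place in a sub-group of clinics within the DI arm. It gives no rating of APRETUDE overall and nothing from the RI arm.

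**3. What Section 2 needs against what Table 3 supplies for overall FIM.**

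| Summary | Required by Section 2 | Possible under Table 3 |
|---|---|---|
| Mean at baseline | yes | no |
| Mean at M7/M6 | yes | no |
| Mean at M13/M12 | yes | yes |
| Change to M7/M6 | yes | no |
| Change to M13/M12 | yes | no |

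Required: 3 means + 2 changes = 5. Possible: 1. Lost: 5 − 1 = 4.

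**4. Does the loss reach the tested hypotheses?** The patient hypothesis in Section 5.1 concerns mean FIM at Month 13, and Section 5.2 sizes the patient sample on that mean, so neither needs a baseline. As a check on Table 7 (62 and 125 patients, d = 0.44, stated power 0.80), assume a two-sided alpha of 0.05, since the protocol states none. The noncentrality is 0.44 × √(62 × 125 / 187) = 2.83. The normal approximation gives Φ(2.83 − 1.96) ≈ 0.81 and the noncentral t gives 0.80. The plan's figure is reproduced and does not depend on the disputed cell. The primary endpoint is a staff measure and is not touched.

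**5. What else carries patient feasibility over time?** The patient ISQ, which Section 5.4 and Table 10 describe as including feasibility items, is scheduled at all three times. It gives related information but not a FIM score.

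**6. Staff interviews.** Table 3 has eight rows for staff interviews. Four list baseline (Fidelity, Awareness, Process evaluation, Perceptions) and four do not (overall and telehealth feasibility, overall and telehealth acceptability).

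**The case against.** The best reply is that Table 3 is only an outline. Sections 4.1.1 and 4.1.2 say that patients complete their assessments according to the schedule of activities, and Section 4.1.3.1 points to the Annexes for the full schedule. The Annexes place patient questionnaires at exactly the three times that Section 2 requires. On that reading the cell is a drafting slip and FIM will be given at every questionnaire visit.

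That may well be what was intended, and the three other complete rows support it. But the Annexes do not say which instruments make up the patient questionnaires at each visit. They show that FIM could be given at baseline and mid-study, not that it will be. The only explicit statement in the protocol says otherwise.

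Three narrower points stand:

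- Section 5.3 reaches patients' change from baseline only by reference to the staff analysis. Sections 2 and 5.4 state it directly, and only Section 2 fixes the time points.
- No hypothesis test is attached to the change scores, and Section 5.4 lists them among the other, not the key, secondary outcomes.
- The staff interview mismatch is minor. A footnote in both Annexes lets interview timing be altered, and the Perceptions row combines interview and questionnaire, so its baseline entry may belong to the questionnaire.

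**Conclusion.** The contradiction is real and should be corrected. If Table 3 is followed as written, four of the five summaries of patients' overall FIM in Section 2 cannot be produced, including both change scores, and the missing baseline cannot be recovered after the first injection. This is conditional on Table 3 governing what is given at each visit; the protocol does not establish that sites will in fact omit FIM. The effect is limited to one instrument in one secondary objective. AIM, ISQ, the telehealth FIM, the Month 13 patient comparison, the primary endpoint and the sample size are unaffected.

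**What to change.** In Table 3, change the time points for patient FIM under Feasibility-Overall to baseline, M7(OLI)/M6(DTI) and M13(OLI)/M12(DTI), and name FIM among the patient questionnaires in Annexes 1 and 2. This costs one table cell and two row labels. FIM joins questionnaires already scheduled at those visits, so no visit is added.

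If FIM at the end of the study alone was intended, the alternative is to remove the baseline, mid-study and change-from-baseline FIM outcomes from Sections 2 and 5.4 and to limit the patient sentence in Section 5.3 to match. That gives up a stated secondary endpoint, and Sections 2, 5.3 and 5.4 all point the other way, so correcting the cell is the natural choice.

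In the same edit, reconcile the staff interview time points between Section 3.3.2, the four Table 3 rows that list baseline, and the Annexes.

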### 3. RESEARCH DESIGN

[figure not shown]
This study will be conducted in accordance with the protocol and with:

- Consensus ethical principles derived from international guidelines including the Declaration of Helsinki and Council for International Organizations of Medical Sciences (CIOMS) International Ethical Guidelines
- Applicable ICH Good Clinical Practice (GCP) Guidelines
- Applicable laws and regulations

#### 3.1. Study Design

This is a Phase 4, randomized, open-label, two-arm study evaluating the impact of two implementation strategy conditions – dynamic implementation and routine implementation – on the delivery of CAB PrEP in low and high-volume PrEP sites in the U.S. for MSM and Transgender men  $\geq 18$  years of age. MSM and transgender men who tested HIV-1 negative at the sites prior to initiation of CAB PrEP (Section 3.2.1) will be enrolled. Approximately eighteen clinics – about 9 high and about 9 low volume – will be randomized 2:1 to either dynamic implementation or routine implementation. This study is being conducted following FDA approval and commercial availability of CAB PrEP in the U.S.

Eligible and consenting PSPs will be followed for 12 calendar months from the time of enrollment and receipt of the first administration of CAB tablets for PrEP oral lead in or APRETUDE (for direct to injection PSPs). The study includes a screening period of up to 90 days to allow sufficient time for any benefit verification checks to be completed, as required. PSPs will be initiated on CAB PrEP as soon as their eligibility is confirmed. The screening period is followed by a 11-month or 12-month administration period of CAB PrEP depending on whether an optional 1-month oral lead-in of CAB tablets for PrEP is administered, followed by APRETUDE IM injections every two months after the one-time loading dose (i.e., first 2 IM doses 1 month apart and 2 months apart thereafter). All PSPs will receive a total of 7 APRETUDE IM injections, with the last IM injection visit being their last study visit. After 11-month (direct to injection) or 12-month (with OLI) treatment period, PSPs will complete the study and will be offered PrEP regimen as per site standard of care. When PSPs complete their M12/M13 assessments, irrespective of missed injections, they will be a completer. Consenting SSPs at the site will participate in study quantitative and qualitative study assessments to evaluate the impact of the two implementation strategy conditions on the feasibility of delivering APRETUDE. When SSPs completes their M13 study assessments, they will be a completer. The end of study is defined when the last PSP and SSP have completed their implementation science assessments. For a detailed Schedule of Activities (SoA) refer to [ANNEX 1](#) and [ANNEX 2](#). CAB PrEP dosing information can be found in the prescribing information for CAB PrEP.

